8.2. STUDY PROCEDURE

The study device is intended to be used in conjunction with a standard EP clinical procedure, such as an EP study or ablation procedure, where life-threatening VT or VF may spontaneously occur or may be induced. Although subjects will undergo a standard EP procedure, it is not anticipated that life-threatening VT or VF will occur or be induced in all subjects.

The Jewel EP Lab System will be set-up prior to initiation of the EP clinical procedure. The subject's torso will be prepared for the placement of the Jewel EP Lab System. If hair is present, it will be trimmed per the hospital's protocols. The areas where the Adhesive Electrode Patches will be cleaned with antiseptic, such as Isopropyl Alcohol prior to being placed on the subject.

The Adhesive Electrode Patches will be placed in the anterior-apical vector, with the upper patch located under the clavicle and lateral to the midline and the lower patch placed so that the 3rd/4th exterior housing junction is at or posterior to the mid-axillary line. The patches shall be placed by aligning the patch and pulling the release liners in order of their number, 1 through 4. After both patches have been placed, the time of device placement will be recorded on the Procedure Case Report Form (CRF). A photograph will be taken to document device location. The photograph will not include the subject's face. The device will be turned on and the time will be recorded on the Procedure CRF.

Hospital-supplied rescue defibrillator pads will be placed on the subject in an anterior-posterior position, ensuring a 1-2 centimeter margin between the defibrillation pads and the Adhesive Electrode Patches. A hospital-supplied ECG will be used per hospital procedure. The Investigator will continue with the planned EP clinical procedure and monitor the subject's heart rhythms per standard hospital protocol.

After the EP clinical procedure commences, the Jewel EP Lab System will be used to terminate the spontaneous or induced life-threatening VT or VF.

Prior to the onset of life-threatening VT or VF, the hospital staff will prepare the Jewel EP Lab System by initiating the device charge cycle. The user will depress the "CHARGE" button on the Controller Box to charge the capacitors for delivery of the defibrillation shock. Charging will take approximately 20 seconds during which the Controller Box will display a flashing green "CHARGE" light. The rescue defibrillator will also be prepared for use should the Jewel EP Lab System not deliver an electrical shock or fail to terminate VT/VF.

Upon completion of charging, the Jewel EP Lab System will display a solid green "CHARGE" light on the Controller Box. After the device is charged, the user will be able to manually deliver a

defibrillation shock through the Jewel EP Lab System by depressing the “SHOCK” buttons on the Controller Box.

Throughout the procedure, the Jewel EP Lab System will continuously monitor the ECG signal, and the Controller Box will illuminate the “DETECT” yellow light to notify the user when the algorithm has detected life-threatening VT or VF. The detection algorithm continuously analyzes the ECG signal in segments of eight seconds and determines whether a shockable rhythm is present in the majority of that segment after the entire segment has finished. Based on the timing of the onset of VT/VF relative to ECG segments, the algorithm may require up to 8-12 seconds of ECG signal to capture a full eight-second segment for determination of a shockable rhythm. If a shockable rhythm is detected, the light indicator on the Controller Box will flash a yellow light continuously. If the VT/VF is sustained through a second eight-second segment, the light indicator will change to a solid yellow light. At any time during this process, irrespective of algorithm determination, the defibrillation shock may be delivered using the “SHOCK” buttons on the Jewel EP Lab System. Although the performance of the detection algorithm is not a primary endpoint in this study, the status of the detection light will be recorded during the case.

In cases where the patient is stable, the VT/VF may be allowed to continue for 20-30 seconds to ensure the algorithm has sufficient ECG data to make a rhythm determination over multiple eight-second segments. The timing of the defibrillation shock is under the discretion of the physician to ensure patient safety. In the case where VT/VF is not sustained for the minimum of 8-12 seconds, the indicator light on the Controller Box will not illuminate. The ECG data recorded on the Jewel EP Lab System will also be analyzed post-procedure to assess the performance of the algorithm.

In the event that the defibrillation shock delivered through the Jewel EP Lab System does not successfully terminate the VT/VF, the rescue defibrillator will be used to deliver subsequent defibrillation shock(s).

Throughout the clinical procedure, the Jewel EP Lab System will only be used in appropriate cases based on physician judgment.

- In the case that a defibrillation shock is delivered through the Jewel EP Lab System, the clinical procedure will continue as planned. If a subsequent defibrillation shock is required during the procedure, the rescue defibrillator will be used. The Jewel EP Lab System will only be employed for a single shock during each procedure. In the case that the Jewel EP Lab System is used to deliver a defibrillation shock and the subject meets all enrollment criteria, the subject will be included in the treatment analysis for the primary endpoint.
- In the case that the Jewel EP Lab System is not used to deliver a defibrillation shock during the procedure, the subject will not be included in the treatment analysis to meet the sample size requirements per the statistical plan. In approximately 30 percent of cases, life-threatening VT or VF may not occur or be inducible and therefore an external defibrillation shock would not be required.¹¹ In addition, based on physician judgment, the Jewel EP Lab System may not be used to provide a defibrillation shock during the procedure. In these cases, the subject will not be included in the treatment analysis for the primary endpoint, however, an Intent-to-Treat (ITT) analysis will be performed for informational purpose.

At the conclusion of the acute procedure, the Jewel EP Lab System will be removed from the subject and the Controller Box will be disconnected from the Adhesive Electrode Patches. The subject will exit the study immediately after completion of the EP clinical procedure.

8.3. FOLLOW-UP

No clinical follow-up is required following the acute procedure, and subjects will exit the study immediately after completion of the procedure unless an adverse event (AE) is observed during the Jewel EP Lab System treatment procedure in which case the subject will be followed until the AE has been resolved.

9. SUBJECT REMOVAL FROM STUDY

Only subjects that meet all enrollment criteria and have received a defibrillation shock will be included in the treatment analysis, however all subjects enrolled, whether or not receiving a defibrillation shock, will be included in the reporting of study results.

Overall, if a subject drops out of the study at any time due to an adverse event or for any other cause, the reason for discontinuation, the nature of the event, and its clinical course must be fully followed and documented. In the case of an adverse event, the Investigator must strive to follow the subject until the adverse event has either resolved, become clinically insignificant, the event is stabilized, or the subject is lost to follow-up.

If at any point during the study, the patient withdraws consent or the Investigator assesses that the risks to the subject outweigh the benefits of participation in the study, the subject will be discontinued. If, during the course of the study, the Investigator feels that, in his/her best clinical judgment, the study should be prematurely terminated, he/she will notify the Sponsor and give the reason(s) for this decision. If the Sponsor decides, based on data or internal information, that it would be prudent to discontinue temporarily or to terminate the study, the Sponsor will inform the Investigator of this decision and the reason(s) for the decision.

10. ASSESSMENT OF SAFETY

The Investigator will carefully monitor each subject throughout the study for possible adverse events. All adverse events must be documented on CRFs designed specifically for this purpose and followed until either completely resolved or until a stable chronic outcome is determined by the Investigator.

The definitions and procedures for reporting adverse events (AE), serious adverse events (SAE), adverse device effects (ADE)/serious adverse device effects (SADE), unanticipated adverse device effects (UADE), and device deficiencies (DD) are presented in the sections below. It is of the utmost importance that all staff involved in the investigation are familiar with the definitions and procedures.

10.1. SAFETY DEFINITIONS

Adverse Event (AE)

An Adverse Event is any unfavorable and unintended sign, symptom, or disease, temporally associated with the use of the Jewel EP Lab System, whether or not it is related to the Jewel EP Lab System.

No causal relationship with the clinical trial product is implied by the use of the term “Adverse Event.” Exacerbations of a pre-existing condition/illness that are defined as a “more frequent occurrence” or as “an increase in the severity of the pre-existing conditions” are considered AEs.

Serious Adverse Event (SAE)

An adverse event is considered “serious” if, in the view of either the Investigator or Sponsor it:

- Results in death;
- Is considered life-threatening (meaning that its occurrence places the subject at immediate risk of death. It does not include an adverse event or suspected adverse reaction that, had it occurred in a more severe form, might have caused death.);
- Requires inpatient hospitalization or prolongation of existing hospitalization;
- Results in persistent or significant incapacity or disability; or
- Results in a congenital anomaly/birth defect.

Adverse Device Effect /Serious Adverse Device Effect (ADE/SADE)

An adverse device effect/serious adverse device effect is any AE that is related to the Jewel EP Lab System. All ADEs/SADEs are further categorized as anticipated or unanticipated by the Sponsor.

Unanticipated Adverse Device Effect (UADE)

A UADE is any serious adverse effect on health or safety or any life-threatening problem or death caused by, or associated with, a device, if that effect, problem, or death was not previously identified in nature, severity, or degree of incidence in the investigational plan or application (including a supplementary plan or application), or any other unanticipated serious problem associated with a device that relates to the rights, safety, or welfare of subjects.

Device Deficiency

A device deficiency is an inadequacy of a medical device related to its identity, quality, durability, reliability, safety or performance, such as a malfunction, misuse or use error, and inadequate labeling.

10.2. REPORTING OF ADVERSE EVENTS

Reports of adverse events will be collected throughout the duration of the study for both the ES-1 and ES-2 models of the Jewel EP Lab System. Adverse events must be documented on the Adverse Event case report form by the Investigator or his/her designee; however, it is the responsibility of the Investigator to ensure that all information is correct.

When reporting AEs/SAEs, the Investigator should include the following information:

1. Description of event (diagnosis)
2. Onset of event
3. Duration of event
4. Severity
5. Relationship to device
6. Action taken
7. Patient outcome

Severity describes the intensity of an event and will be assessed as:

Mild – The AE does not interfere in a significant manner with the subject's normal functioning level and requires minimal or no treatment.

Moderate – The AE produces some impairment of function, but is not hazardous to health.

Severe – The AE produces significant impairment of function or incapacities and/or is a hazard to the subject. These events may require systemic therapy or other treatment.

All AEs will be assessed for relationship to the Jewel EP Lab by the Investigator who examines and evaluates the participant, based on temporal relationship and his/her clinical judgment. The degree of certainty about causality will be graded using the categories below:

Definitely Related – There is clear evidence to suggest a causal relationship, and other possible contributing factors can be ruled out. The clinical event occurs in a plausible time relationship to use of the study device and cannot be explained by concurrent disease or other drugs or chemicals.

Probably Related – There is evidence to suggest a causal relationship, and the influence of other factors is unlikely. The clinical event occurs within a reasonable time after use of the study device, is unlikely to be attributed to concurrent disease or other drugs or chemicals.

Potentially Related – There is some evidence to suggest a causal relationship, however, other factors may have contributed to the event (e.g., the participant's clinical condition, other concomitant events). Although an AE may rate only as "possibly related" soon after discovery, it can be flagged as requiring more information and later be upgraded to "probably related" or "definitely related", as appropriate.

Unlikely to be Related – A clinical event, including an abnormal laboratory test result, whose temporal relationship to use of the study device makes a causal relationship improbable (e.g., the event did not occur within a reasonable time after use of the study device) and in which other drugs or chemicals or underlying disease provides plausible explanations.

Not Related – The AE is completely independent of use of the study device, and/or evidence exists that the event is definitely related to another etiology. There must be an alternative, definitive etiology documented by the clinician.

All SAEs must be reported to the Sponsor within 24 hours of learning about the event, regardless of the time that may have elapsed from the time the event occurred. The Sponsor must also receive a completed Adverse Event CRF within three (3) working days of the Investigator being notified of the event and should include the Investigator's assessment of the event, action that is required, results of any diagnostic tests that were performed, a description of any treatment implemented, a statement of the subject's current clinical status, and the Investigator's signature and date. Investigators shall comply with all local reporting requirements.

All device deficiencies (ES-1, ES-2) shall be documented and reported to the Sponsor without unnecessary delay.

If required, the Sponsor should inform the Competent Authorities about all SAEs and device deficiencies that may have led to a SADE associated with the device, as per local requirements.

The Sponsor is responsible for relaying adequate information on all UADEs to all participating Investigators. Regulatory authorities will be informed of all UADEs by the Sponsor. The Sponsor is also responsible for assessing whether a UADE poses an unreasonable risk to patients if the study is continued.

10.3. FOLLOW-UP OF PATIENTS AFTER ADVERSE EVENTS / SERIOUS ADVERSE EVENTS

In the case that an AE is observed during the Jewel EP Lab System treatment procedure, the subject will be followed until the AE is resolved or the Investigator decides that the AE is stable and needs no further follow-up. The date when the Investigator considers one of these outcomes to have occurred for the AE will be considered the last visit for the subject, and the outcome should be recorded on the appropriate case report form.

11. STATISTICS

11.1. STATISTICAL ANALYSIS AND SAMPLE SIZE RATIONALE

A prospective Statistical Analysis Plan has been developed for this study. Specific information regarding the planned statistical analysis is presented below.

The VEST trial was a randomized controlled trial (RCT), the design of which controls for the bias inherently present in retrospective registries. VEST reported the real-world LifeVest performance in over 2,300 subjects. The results of the VEST trial were presented at the American College of Cardiology Conference in March 2018, and were published in the New England Journal of Medicine on 27 September 2018. In this RCT, there were a total of 21 appropriate shocks, of which 13 were converted with the first shock and 8 of which required ≥ 2 shocks (38%). This translates into a 62% first shock success rate.¹⁰ Of the 21 subjects who received an appropriate shock, 15 subjects (71%) survived. There were 25 sudden deaths in the LifeVest arm, 9 of which were wearing the LifeVest at the time of death, suggesting that there were a fair number of deaths that likely should have been prevented through use of the LifeVest.¹⁰ Taken together, these RCT data suggest that the true results when using the LifeVest are potentially much lower than typically reported in registries.

Prior to the start of the VEST trial, the VEST protocol estimated that WCD conversion success rate would be 79.7%. The VEST trial was powered for mortality, not conversion success, so there were no power calculations around this endpoint. As the results of the VEST RCT demonstrated a first shock conversion success rate of 62%, this first shock conversion success rate for LifeVest will be the performance goal for the EP Lab Study, meaning that when the confidence interval is calculated from the observed first shock conversion success rate for the Jewel, the Jewel lower confidence bound will be greater than 62%, which will mean that the Jewel results are better than LifeVest's point estimate.

Utilizing the observed 62% first shock conversion success rate seen with the LifeVest in the RCT as the EP Lab Study performance goal provides assurance that the performance of the Jewel is aligned to the real-world performance of LifeVest.

For the calculation of sample size, this study will use an anticipated first shock conversion success rate of 87.5% in the EP Lab Study with a performance goal of 62%, the same as the first shock success rate seen in VEST. The performance of the Jewel will be considered acceptable if the lower confidence limit exceeds the performance goal of 62% (green line in the graph on page 24).

The sample size for this study is a maximum of 24 subjects. Subjects can be treated with either the ES-1 or the ES-2 model of the Jewel EP Lab System, as the devices are representative of each other. This sample size is based on a group sequential design measuring the observed proportion of successful life-threatening VT or VF terminations. The group sequential design uses a Pocock alpha spending function and allows for testing after 12, 18, and 24 subjects are enrolled. The design controls the overall Type I error rate at 5%. In line with the Pocock alpha spending function, a one-sided lower 97.4% exact confidence bound will be calculated using the exact binomial (Clopper-Pearson) method at each testing point.

Primary Endpoint Analysis:

Upon completion of the Jewel EP Lab Study, all clinical data from both the ES-1 and ES-2 models of the Jewel EP Lab System will be pooled, as the devices are representative of each other. The primary endpoint will evaluate the percent of successful terminations of life-threatening VT or VF in subjects who are in subjects who are enrolled in compliance with the protocol-defined entry criteria and treated with the Jewel EP Lab System (either ES-1 or ES-2 model).

Using the VEST RCT results for the first shock success as a guide, the performance goal of 62% was established for the Jewel EP Lab Study. The endpoint will be achieved if the lower confidence limit exceeds the performance goal of 62% using a one-sided lower 94.5% exact confidence bound at one of the three testing points.

These conditions ensure that performance will be in line with previously published randomized controlled trial results on a relevant comparator, the ZOLL LifeVest which, is the only commercially approved WCD in Europe or the US. The method for testing the conversion success will follow these steps:

1. If after attempting to convert the first 12 subjects, all subjects have been successfully converted (100% conversion rate) the trial will be stopped and deemed a success. Otherwise, continue to Step 2.
2. If conversion is less than 100% after 12 total subjects, enroll six (6) additional subjects for a total of 18 subjects. If 17 out of the 18 are successfully converted (94.4% conversion rate), or if 16 out of the 18 are successfully converted (88.0% conversion rate), the trial will be stopped and deemed a success. Otherwise, continue to Step 3.
3. Enroll the final six (6) subjects for a total of 24 subjects. If after attempting to convert 24 subjects, 21 of the 24 are successful (87.5% conversion rate), the trial will be deemed a success.

A 100% conversion rate with 12 subjects results in a one-sided lower 97.4% exact confidence bound of approximately 73.7% which exceeds the 62% performance goal.

[figure not shown]
With a sample size of 18 subjects with 1 failure, the conversion rate is 94.4% with a one-sided lower 97.4% exact confidence bound of approximately 72.8% which also exceeds the 62% performance goal.

With a sample size of 18 subjects with 2 failures, the conversion rate is 88.9% with a one-sided lower 97.4% exact confidence bound of approximately 65.4% which also exceeds the 62% performance goal.

With a sample size of 24 subjects with 3 failures, the conversion rate is 87.5% with a one-sided lower 97.4% exact confidence bound of approximately 67.8% which also exceeds the 62% performance goal.

All of these scenarios result in a successful trial as the one-sided lower 97.4% exact confidence bound is above the performance goal of 62%. If at any point during the course of this study there are more than three (3) failures to convert a shockable rhythm (life-threatening VT or VF) due to the Jewel, the study will be stopped and deemed unsuccessful.

The graph below summarizes the group sequential study design, conversion success, and results of the one-sided lower 97.4% exact confidence bound.

Overall Type I Error Discussion:

The group sequential design of the Jewel EP Lab Study is meant to control the overall Type I error rate with 90% power. This design uses a Pocock alpha spending approach which controls the overall Type I error rate at 5%. The group sequential design of the Jewel EP Lab Study is being used in order to reduce the number of subjects put at risk through early stopping rules, while still providing sufficient data to demonstrate the effectiveness of the Jewel EP Lab System to successfully convert life-threatening VT and VF. Preliminary testing points and alpha expenditures were estimated using SAS version 9.3 which employs a normal approximation to designing sequential trials. The alpha spent at each testing point was used to determine the confidence level of the exact lower confidence bound. These confidence levels were then used to adjust the testing points to accommodate exact methods rather than the normal approximation. Simulations of 3000 trials of size 24 were used to confirm that the Type I error rate was controlled at the 5% level.

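### The 97.4% level is Pocock's constant boundary, not the spending function named as its source, and the written rule has exact power of 70.5%, not 90%

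*Combined protocol and SAP*

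**What the plan says.** All of this is in Section 11.1 of the combined protocol and SAP unless noted.

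- Method and looks: "The group sequential design uses a Pocock alpha spending function and allows for testing after 12, 18, and 24 subjects are enrolled". Overall error: "The design controls the overall Type I error rate at 5" per cent.
- Level: "In line with the Pocock alpha spending function, a one-sided lower 97.4% exact confidence bound will be calculated" by the Clopper-Pearson method at every look. Section 6.1 also uses 97.4%.
- Derivation (Overall Type I Error Discussion): "The alpha spent at each testing point was used to determine the confidence level of the exact lower confidence bound".
- A second level, under Primary Endpoint Analysis: success is judged "using a one-sided lower 94.5% exact confidence bound at one of the three testing points".
- Counts: at 12 subjects, if "all subjects have been successfully converted (100% conversion rate) the trial will be stopped and deemed a success"; otherwise continue. At 18 subjects, 16 or 17 conversions succeed. At 24 subjects, 21 conversions succeed. More than three failures due to the device end the study as unsuccessful.
- Operating characteristics: 90% power, with a planned conversion rate of 87.5% and a goal of 62%. The looks were first set by a normal approximation and then adjusted for exact methods. Type I error was checked with 3000 simulated trials.

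**The concern.** A Pocock alpha spending function and Pocock's constant boundary are different methods. They coincide only roughly, and less well when the looks are unequally spaced, as here (half, three quarters and all of the information). A statistician who follows the named function will not arrive at 97.4%, so the stated derivation cannot be reproduced.

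The stated operating characteristics are the larger matter. The final rule is a set of exact counts, yet the power figure sits beside a normal-approximation design and a simulation reported only as confirming 5%. If the counts have other properties, the ethics committee and the sponsor are judging the trial on a chance of success it does not have. The stray 94.5% adds a second written criterion that disagrees with the counts.

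**Working it through.** **Inputs (Section 11.1).** Looks at n = 12, 18, 24, so t = 0.50, 0.75, 1.00. Overall alpha 0.05, taken as one-sided because the bound is one-sided. Goal 0.62, planned rate 0.875. Success counts 12, 16, 21.

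**1. Reproduce 97.4%.** The constant boundary c solves P(any Z_k ≥ c) = 0.05, where the Z_k are standard normal with correlation √(t_i/t_j). This gives c = 1.947 and nominal p = 0.0258, that is 97.4%. At the unrounded 97.42%, the Clopper-Pearson lower bounds are:

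| Result | Recomputed | Plan |
|---|---|---|
| 12/12 | 73.72% | 73.7% |
| 17/18 | 72.85% | 72.8% |
| 16/18 | 65.44% | 65.4% |
| 21/24 | 67.77% | 67.8% |

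The plan's level and all four bounds reproduce.

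**2. The function named.** The plan prints no formula. The standard Pocock-type function is α·ln(1 + (e − 1)t). Cumulative spend is 0.0310, 0.0414, 0.0500. The boundaries are z = 1.866, 2.004, 2.009, with nominal p = 0.0310, 0.0226, 0.0223. The levels are 96.9%, 97.7%, 97.8%; none is 97.4%.

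**3. Exact Type I error of the written counts (p = 0.62).** S_n is the number converted among n; B6 is binomial with 6 trials.

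- Look 1: 0.62^12 = 0.00323.
- Look 2: P(S_18 ≥ 16) − P(S_12 = 12)·P(B6 ≥ 4) = 0.01274 − 0.00323 × 0.5857 = 0.01085.
- Look 3 is reached successfully only from 15/18 followed by 6/6: [P(S_18 = 15) − P(S_12 = 12)·P(B6 = 3)] × 0.62^6 = (0.03443 − 0.00323 × 0.2616) × 0.0568 = 0.00191.
- Total: 0.00323 + 0.01085 + 0.00191 = 0.01598, or **1.6%**.

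A run of 3000 simulated trials gave 1.5%, in agreement.

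**4. Exact power (p = 0.875), same formulas.**

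- Look 1: 0.875^12 = 0.2014.
- Look 2: 0.6051 − 0.2014 × 0.9709 = 0.4096.
- Look 3: (0.2150 − 0.2014 × 0.0262) × 0.4488 = 0.0941.
- Total: 0.7051, or **70.5%**. At a true rate of 90% it is 82.5%.

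The failure stop changes neither total, because every successful path has at most three failures. The stated 90% was not reproduced: a normal approximation with the constant boundary at n = 24 gives 78% with the null variance and 97% with the alternative variance.

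**5. Where the shortfall comes from.**

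| Counts | Type I error | Power at 87.5% |
|---|---|---|
| 12/16/21 (written) | 1.6% | 70.5% |
| 12/16/20, no failure stop | 2.75% | 83.7% |
| 11/16/21 | 3.3% | 74.1% |
| 11/16/20, no failure stop | 4.25% | 85.1% |

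20/24 already clears 62% at 97.4% (bound 62.8%), but it means four failures. Moving only the last count gives 83.7 − 70.5 = 13.2 points of power. Moving look 1 to 11/12, as the 96.9% level would allow, then adds 85.1 − 83.7 = 1.4 points, or 74.1 − 70.5 = 3.6 points with 21/24 kept. The rest of the gap to 5% and 90% reflects discreteness and the normal approximation.

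**6. The 94.5% sentence.** At 94.5% the bound is 66.8% for 11/12 and 62.9% for 15/18. Both pass; the written counts say continue. The lowest passing counts would be 11/15/20, with exact Type I error of 6.2%, or 5.7% with the failure stop. Either exceeds 5%.

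**The case against.** The case for leaving the text alone is substantial. The counts are explicit, the quoted bounds match them, and the rule is conservative. Nobody applying Step 1 could declare success at 11/12. The plan also speaks of "This design uses a Pocock alpha spending approach which controls the overall Type I error rate at 5" per cent, and *approach* could loosely cover the constant boundary. This defends the rule, and that part stands. It does not defend the stated derivation, the 90% power or the 94.5% sentence.

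A reader might infer more than the documents support:

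- *That 97.4% is an invalid level.* It is the correct constant Pocock boundary for these looks.
- *That 1.6% contradicts the plan.* The plan says the error is controlled at 5%, not fully spent, and 1.6% satisfies that.
- *That the label reverses the result at 11/12.* The bound is 62.9% at 96.9% and 61.8% at 97.4%, and 11/12 has probability 34.5% at the planned rate. But the written outcome is to continue, not to fail. From 11/12, later success has probability 0.8335 (at least 5 of the next 6) + 0.1374 × 0.4488 (4 of 6, then 6 of 6) = 89.5%. So about 34.5% × 10.5% = 3.6% of trials would end differently.
- *That the counts must therefore be loosened.* Most of the power gain would come from 20/24, which the three-failure stop bars. Relaxing a prespecified rule to fit a label would raise the false-success risk. It could also look data-driven, since Section 3.3 (ES-2 for newly enrolled subjects) and the pooling of models suggest that some subjects have already been treated.

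**Conclusion.** The point holds as a fault of description, not of error control. The named spending function does not give 97.4%; the constant Pocock boundary does. The written rule has exact one-sided Type I error of 1.6% and exact power of 70.5%, about 20 points below the stated 90%. At the planned rate the trial would miss its endpoint in roughly three cases in ten, where the plan implies one in ten. The 94.5% sentence contradicts the counts and, used as a rule, would exceed 5%.

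Assumptions: the 5% is one-sided; the looks count treated subjects; outcomes are independent with a common success rate; every non-conversion counts as a failure due to the device; and the spending function is the standard formula, which the plan does not print. The exact error and power depend only on the written counts, not on that formula.

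**What to change.** Keep the written counts and, in Section 11.1:

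1. Call the boundary a constant Pocock boundary at one-sided 97.4% for looks at 12, 18 and 24, and remove the statement that alpha spent at each look set the level.
2. Replace the claims resting on the normal approximation and the 3000 simulations with exact figures: Type I error 1.6% at 62%, power 70.5% at 87.5%.
3. Reconcile the 94.5% sentence under Primary Endpoint Analysis with the 97.4% used in Section 6.1 and elsewhere in Section 11.1.
4. Correct the rate for 16/18 in Step 2 from 88.0% to 88.9%, as given later in the same section. This is a typing error; the rule uses the count.

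The cost is a text change and a short calculation, with no added subjects. The downside is that the stated power becomes less favourable. Moving the cut-offs to 11/12 or 20/24 is optional. It would need its own justification, including how 20/24 fits with the failure stop, and is not required to settle this point.
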